# Confidentiality and Privacy:

Currently all data for patients undergoing bariatric surgery are kept confidential The data will be collected from electronic medical records from Advanced Laparoscopic Surgical Associates (ALSA) surgical group and through EPIC.

# Data Security:

All data will be maintained on a firewall and password protected shared drive maintained by investigators, sub investigators, and clinical staff. Patients assigned to randomized treatment group will have patient identifier label and entered into secure database by study coordinator. Patient label and study assignment will be placed into a secure locked box and collected at end of each operating day. The information will be entered by the study coordinator or study staff and the patient label and randomization cards will be placed in secure CMC vendor approved shredding boxes immediately afterwards. This will be completed daily and by 1-2 assigned study staff who will maintain chain of custody of patient information. Patient questionnaires and dairies will also be collected and stored following HIPAA regulation and locked in secure room.

Data collection, information from patient diaries and questionnaires from ALSA and data collection from CMC electronic health records will be placed on password protected file on Fresno Heart and Surgical hospital server drive with limited rights access. All patient information will be de-identified prior to analysis. The data safety monitoring monitor (DSM) will meet (in person or via conference call) following enrollment of 100 subjects and will have access to only de-identified data.

All data collected during the study that contains any patient identifiers will be destroyed upon completing the publications relevant to this study. Data that is stored electronically will be erased from all electronic storage locations. Any paper records that are collected will be destroyed via shredding using a CMC approved vendor.

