#### **Randomization:**

If the patient chooses to participate, they will be randomized to 2 arms of either liposomal bupivacaine also known as Exparel® group, or bupivacaine only group on the day of surgery before anesthesia induction in the operating room.

The randomization will be in a 1:1 ratio. The patient and operating surgeon will not be notified which arm the patient is in. The randomization will be done by choosing an envelope in a stack that is previously randomized in a 1:1 ratio by computer program generator. The card in the envelope will state the assigned treatment arm. This will be relayed only to the operating room surgical tech. The randomized card will have an attached patient label and be placed into a locked container for later retrieval by study coordinator and entered into database by end of the operating day. The study coordinator will have access to decode each patient in the study for medical necessity.

The operating room surgical techs and nurses will then prepare the medications and cover the syringes containing the medications with colored sterile tape. Surgical techs and nurses responsible for preparing the medications will verify the medications and doses with one another before covering the syringe with sterile tape. This will impede the surgeon from guessing medication type as liposomal bupivacaine is slightly opaque. All syringes and containers containing study medications will be labeled appropriately with either 1.3% bupivacaine and/or 0.25% bupivacaine and normal saline. The Surgical techs and nurses will announce the medications as "study medications" when delivered to the surgeon and during "Time-Out" procedures. This is in compliance

with CMC Operating Room Policy and Procedure Number 11142.

Once medications are mixed and placed into masked syringes, the surgeon may enter the operating room. At the beginning of the surgery, the patient will be administered local surgical site injections of the assigned medications.

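### The labelled randomisation cards, the only stated source record of each patient's drawn arm, go for shredding right after same-day entry, and no other way to verify the entered arm is stated

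*Combined protocol and SAP*

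**What the plan says.** The Randomization section describes how an arm is assigned: "The randomization will be done by choosing an envelope in a stack that is previously randomized in a 1:1 ratio by computer program generator". It continues: "The card in the envelope will state the assigned treatment arm". On the link to the patient it says: "The randomized card will have an attached patient label and be placed into a locked container for later retrieval by study coordinator", and the assignment is to be "entered into database by end of the operating day".

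Data Security then states what happens to the paper. Once the information has been entered, the patient label and "randomization cards will be placed in secure CMC vendor approved shredding boxes immediately afterwards". On staffing it adds: "This will be completed daily and by 1-2 assigned study staff who will maintain chain of custody of patient information".

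The entered arm has a use beyond the analysis. The Randomization section says: "The study coordinator will have access to decode each patient in the study for medical necessity".

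The same Data Security section treats other identifiable paper differently. Questionnaires and diaries are kept in a locked room, and data carrying identifiers are destroyed only once the publications are complete.

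**The concern.** Treatment arm is the one variable on which every comparison depends, including the interim analysis at 100 randomised patients. The database value is a transcription of the card. Once the card has gone for shredding, no stated record remains against which the transcription can be checked. If someone enters the wrong arm and does not notice the same day, the patient is analysed in the wrong group. A coordinator who decodes that patient from the database would also get the wrong answer.

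Errors of this kind, if equally frequent in both arms, pull the estimated difference toward zero. They also leave the final dataset without a source document for its most important field. This follows from a disposal rule that the plan states, so changing that rule is enough to cure it.

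**Working it through.** The point rests on comparing sections of the combined protocol and SAP. The arithmetic at the end is illustration only.

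**Could any other stated record verify the entered arm?**

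- *Computer-generated sequence (Randomization).* The stack was randomised by a program. The documents do not say whether the list is kept, whether the envelopes are numbered, or whether they are used in order. As written, no link from a list line to a patient is described.
- *Drug check by techs and nurses (Randomization).* They verify drug and dose with one another before the syringes are covered. This covers preparation, not the later database entry.
- *Syringe labels (Randomization).* Syringes and containers are labelled with their contents, but nothing says that a label or preparation log is kept.
- *Quality assurance review (Data Safety Monitoring and Reporting Plan).* It applies to submitted clinical data. Allocation is not mentioned, and no source for it is named.
- *Study data file (same section).* Consents and adverse event reports are named as contents. The card is not.
- *Electronic medical records (Confidentiality and Privacy).* They are a data source, but nothing says they hold the study drug given. If they did, they would show treatment received, and could not separate an entry error from a preparation error.
- *Wristband (Study Methods and Procedures).* All patients wear the Exparel band, so it does not distinguish the arms.

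None of these is described as a check on the entered arm. Neither double entry nor a second-person check is stated.

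**Size, under assumptions**

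Inputs from the documents: 100 per arm (Sample Size); power 0.90, alpha 0.05 and an 11-unit difference (Statistical Analysis). No SD and no error rate is given, so the SD is solved from the plan's own power statement and the error rates e are assumed.

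1. Implied SD = 11 / [(z_alpha + z_0.90) × √(2/100)].
   - Two-sided: 11 / (3.2415 × 0.14142) = 24.0.
   - One-sided: 11 / (2.9264 × 0.14142) = 26.6.
   - Both are shown because the stated hypothesis is directional but the sidedness of alpha is not given. By construction, both return power 0.90 at 11 units.
2. If a fraction e of each arm is recorded in the other arm, each recorded mean is a mixture of the two true means. The difference becomes 11 × (1 − 2e). The SD is held fixed.
3. Power = Φ(difference / [SD × √(2/100)] − z_alpha).

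| e | Difference | Power, two-sided | Power, one-sided |
|---|---|---|---|
| 1% | 10.78 | 0.888 | 0.889 |
| 2% | 10.56 | 0.875 | 0.878 |
| 5% | 9.90 | 0.831 | 0.839 |

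At e = 1%, 200 × 0.01 = 2 patients would be expected in the wrong arm, and the chance of at least one is 1 − 0.99^200 = 0.87.

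**The case against.** The strongest reply is that the documents are silent on several points, and silence is not absence. A reader might infer that allocation errors could never be found or corrected. The text does not support that. An error noticed during same-day entry can be put right. A retained list tied to numbered envelopes, or a record of the drug given, might expose others; the documents neither provide for these nor rule them out. Nor do they say that each arm is entered only once, or when the contents of the shredding boxes are destroyed.

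A reader might also blame the shredding for undetected label swaps and redrawn envelopes. That does not follow. A label placed on the wrong card would stay wrong on a retained card, and a redrawn envelope would leave only the card finally used. Retention by itself exposes entry errors. Redraws need envelope numbering and sequential use, which is a separate matter.

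Prompt disposal plausibly serves privacy and blinding, since the cards join identity to arm in a double-blind trial. That is a fair reason to restrict access. It is a weak reason for same-day disposal, because the plan already keeps identifiable diaries under lock and destroys identified data only after publication.

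Finally, the power figures rest on assumed error rates and a back-solved SD. They do not show a large effect and are not evidence that errors will occur.

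**Conclusion.** The point holds in a limited form. The plan sends the only stated source record of each patient's drawn arm for shredding immediately after same-day entry, and states no other means of verifying the entered arm. A mistyped arm could therefore go undetected in the analysis and in an emergency decode.

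The main harm is the lost audit trail. The illustrated cost in power is about 0.01 at a 1% error rate, 0.02 to 0.03 at 2%, and 0.06 to 0.07 at 5%. This assumes that the plan's power statement is correct, that there are 100 patients per arm, and that errors are equally frequent in both arms and unrelated to outcome. The documents do not show that any error will occur, or that one could never be found. This is a cheap improvement rather than a flaw that invalidates the design, but it should be made before enrolment because discarded cards cannot be recovered.

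**What to change.** In Data Security, replace immediate shredding of the labels and cards with retention:

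1. Keep the labelled cards in locked storage, with access limited to the unblinded study staff.
2. Check every entered arm against its card before database lock, and record that this was done. For patients in the interim analysis, do so before that analysis. Until then, the retained card can also be used to confirm an emergency decode.
3. Destroy the cards with the other identified records after publication, under the rule already in Data Security.

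As a separate safeguard against redrawn envelopes, add to Randomization that envelopes are numbered in list order and used in sequence, and that the number is entered with the arm.

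The cost is a short text change, locked storage of a kind the plan already uses, and a brief check of about 200 cards. The downside is that cards linking identity to arm are held for longer, so the access restriction must be written down and kept.

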#### **Transition from research participation:**

All subjects will continue to receive standard of care.

#### Adverse Reaction and Adverse Event Reporting:

Throughout the course of the study, all efforts will be made to remain alert to possible adverse experiences or unanticipated findings. If adverse experiences occur, the first concern will be the safety and welfare of the patient, and appropriate medical intervention will be made. Any adverse reactions observed by the Investigator or reported by the patient, regardless of severity, will be recorded in the patient's case file and reported to the IRB.

Any patients who are discontinued from the study due to adverse experiences will be followed until their medical outcome is determined, and written reports will be provided to the IRB by the Investigator.

#### Funding Section:

No outside source of funding is available to support healthcare expenditures for patients participating in this research study. Coverage for health care expenditures will be sought from each patient's health insurance carrier as per current practice for bariatric. Liposomal bupivacaine (Exparel®) and bupivacaine are FDA approved medications for surgical site infiltration and are included in the bundled cost for bariatric surgery. No extra costs will be charged to the patient. There are no specific costs related to research and therefore no extra funding is required for participation in this study. No additional laboratory testing or imaging will be required to participate in the study. The

investigators and clinical staff involved in the study have no relevant financial disclosures to provide.

